4.1. Protocol Deviations

Important protocol deviations (including deviations related to study inclusion/exclusion criteria, conduct of the trial, patient management or patient assessment) will be summarised and listed.

Protocol deviations will be tracked by the study team throughout the conduct of the study in accordance with the Protocol Deviation Management Plan (Version 4.0, 01 Feb 18)

- Data will be reviewed prior to unblinding and freezing the database to ensure all important deviations are captured and categorised on the protocol deviations dataset.
- This dataset will be the basis for the summaries and listings of protocol deviations.

A separate summary and listing of all inclusion/exclusion criteria deviations will also be provided. This summary will be based on data as recorded on the inclusion/exclusion page of the eCRF.

5. CONSIDERATIONS FOR DATA ANALYSES AND DATA HANDLING CONVENTIONS

5.1.	Study Treatment & Sub-grou	up Display Descriptors

Treatment Group Descriptions											
	RandAll NG	Data Displays for Reporting									
Code	Description	Description	Order in TLF								
Р	Placebo TID Single Dose	Placebo	1								
Q	Placebo BID Single Dose	Placebo	1								
Α	GSK2982772 120 mg TID Single Dose	GSK 120 mg TID	2								
В	GSK2982772 240 mg TID Single Dose	GSK 240 mg TID	3								
С	GSK2982772 360 mg BID Single Dose	GSK 360 mg BID	4								
R	Placebo TID Repeat Dose	Placebo	1								
S	Placebo BID Repeat Dose	Placebo	1								
D	GSK2982772 120 mg TID Repeat Dose	GSK 120 mg TID	2								
E	GSK2982772 240 mg TID Repeat Dose	GSK 240 mg TID	3								
F	GSK2982772 360 mg BID Repeat Dose	GSK 360 mg BID	4								
G	GSK2982772 Cohort 3 Repeat Dose	GSK 120 mg TID	2								
н	GSK2982772 Cohort 4 Repeat Dose	GSK 240 mg TID	3								
J	GSK2982772 Cohort 5 Repeat Dose	GSK XX mg TID/BID ^[1]	3 or 4								
Т	Placebo Cohort 3 Repeat Dose	Placebo	1								
U	Placebo Cohort 4 Repeat Dose	Placebo	1								
V	Placebo Cohort 5 Repeat Dose	Placebo	1								

NOTES:

^[1] Dose level not required as the study met the PK stopping criteria at the end of Cohort 4.

5.2. Baseline Definitions

For all endpoints (except as noted in baseline definitions) the baseline value will be the latest pre-dose assessment with a non-missing value, including those from unscheduled visits. If time is not collected, Day 1 assessments are assumed to be taken prior to first dose and used as baseline.

For Part A, baseline definitions defined in the table are applicable to each treatment period.

Unless otherwise stated, if baseline data is missing no derivation will be performed and baseline will be set to missing. The mean of triplicate measurements at any given time point will be used as the value for that time point unless otherwise stated.

Parameter	Study Asses	Study Assessments Considered as Baseline												
	Screening	Day -1	Day 1 (Pre-Dose)	Data Display										
Safety														
Clinical Chemistry/ Haematology/ Urinalysis	Х	Х	X	Day 1										
12-lead ECG [1]	Х	Х	Х	Day 1										
Vital Signs	Х	Х	Х	Day 1										
C-SSRS (Part B only)	Х		Х	Day -1/Day 1										
Pharmacokinetic	·													
PK Concentrations/ Parameters			Х	Day 1										

NOTES:

^[1] ECG recordings will be performed in triplicate at screening. Use the mean of the triplicate measurements.

5.3. Multicentre Studies

This is a single centre study.

5.4. Examination of Covariates, Other Strata and Subgroups

There are no covariates, strata or subgroups to be investigated in this study.

5.5. Multiple Comparisons and Multiplicity

No adjustments for multiplicity will be required.

5.6. Other Considerations for Data Analyses and Data Handling Conventions

Other considerations for data analyses and data handling conventions are outlined in the appendices:

Section	Component
10.1	Appendix 1: Protocol Deviation Management and Definitions for Per Protocol Population
10.2	Appendix 2: Schedule of Activities
10.3	Appendix 3: Assessment Windows
10.4	Appendix 4: Study Phases and Treatment Emergent Adverse Events
10.5	Appendix 5: Data Display Standards & Handling Conventions
10.6	Appendix 6: Derived and Transformed Data
10.7	Appendix 7: Reporting Standards for Missing Data
10.8	Appendix 8: Values of Potential Clinical Importance
10.9	Appendix 9: Abbreviations & Trademarks
10.10	Appendix 10: List of Data Displays
10.11	Appendix 11: Example Mock Shells for Data Displays

6. SAFETY ANALYSES

All safety analyses will be based on the" Safety" population, unless otherwise specified.

6.1. Adverse Events Analyses

Adverse events analyses including the analysis of adverse events (AEs), Serious (SAEs) and other significant AEs will be based on GSK Core Data Standards. The details of the planned displays are provided in Appendix 10: List of Data Displays.

6.2. Clinical Laboratory Analyses

Laboratory evaluations including the analyses of Chemistry laboratory tests, Hematology laboratory tests, Urinalysis, and liver function tests will be based on GSK Core Data Standards. The details of the planned displays are in Appendix 10: List of Data Displays.

Additionally, plasma 4β -hydroxycholesterol to cholesterol ratio pre-treatment and following 14 days of repeat dosing of GSK2982772 will be summarised and listed.

In addition to GSK Core Data Standards, lipids (Total Cholesterol, Triglycerides, HDL cholesterol, LDL cholesterol and Total Cholesterol/HDL ratio) outside the normal range and percent change in lipids will be summarised. The fasting lipid status will be included in listings.

6.3. Other Safety Analyses

The analyses of non-laboratory safety test results including ECGs and vital signs will be based on GSK Core Data Standards, unless otherwise specified. Suicide risk monitoring including analyses of Colombia Suicide Severity Rating Scale (C-SSRS) will be based on GSK Core Data Standards, unless otherwise specified. The details of the planned displays are presented in Appendix 10: List of Data Displays.

7. STUDY POPULATION ANALYSES

7.1. Overview of Planned Study Population Analyses

The study population analyses will be based on the "Safety" population, unless otherwise specified.

Study population analyses including analyses of participant's disposition, protocol deviations, demographic and baseline characteristics, concomitant medication, and exposure and treatment compliance will be based on GSK Core Data Standards. Details of the planned displays are presented in Appendix 10: List of Data Displays.

8. PHARMACOKINETIC ANALYSES

8.1. Primary Pharmacokinetic Analyses

8.1.1. Endpoint / Variables

8.1.1.1. Drug Concentration Measures

Refer to Appendix 5: Data Display Standards & Handling Conventions (Section 10.5.3 Reporting Standards for Pharmacokinetic).

8.1.1.2. Derived Pharmacokinetic Parameters

Pharmacokinetic parameters will be calculated by standard non-compartmental analysis according to current working practices and using the currently supported version of WinNonlin. All calculations of non-compartmental parameters will be based on actual sampling times. Pharmacokinetic parameters listed will be determined from the plasma concentration-time data, as data permits.

Parameter	Parameter Description
AUC ₍₀₋₂₄₎	Area under the curve from time zero hours to 24 hours
AUC(0-7)	Area under the curve from time zero hours to 7 hours (TID only)
AUC(7-14)	Area under the curve from time 7 hours to 14 hours (TID only)
AUC(14-24)	Area under the curve from time 14 hours to 24 hours (TID only)
AUC(0-12)	Area under the curve from time zero hours to 12 hours (BID only)
AUC(12-24)	Area under the curve from time 12 hours to 24 hours (BID only)
Cmax	Maximum observed concentration after 1 st , 2 nd and 3 rd dose in Part A and on Day 14 in Part B
Tmax	Time to maximum observed concentration after 1 st , 2 nd and 3 rd dose in Part A and on Day 14 in Part B
C ₀	Concentration at zero hours (pre-dose)
C ₇	Concentration at 7 hours post-dose (TID only)
C ₁₂	Concentration at 12 hours post-dose (BID only)
C ₁₄	Concentration at 14 hours post-dose (TID only)
C ₂₄	Concentration at 24 hours post-dose

NOTES:

• Additional parameters may be included as required.

8.1.2. Summary Measure

- The PK of TID and BID dosing on Day 1 in Part A will be evaluated. In Part B the comparisons of interest will be:
 - The PK profile following the 1st dose of the day following administration in the fed state (standard meal on Day 9 and high fat meal on Day 11) or in the fasted state (Day 14).
 - The pharmacokinetic profile following the 1st dose on Day 14 (fasted) and the 1st dose on Day 1 (fasted);

Descriptive statistics (n, arithmetic mean, standard deviation [SD] standard error [SE], 95% CI, minimum, median and maximum) will be calculated by treatment for all PK concentrations over time and for the derived PK parameters. In addition, for loge-transformed PK parameter variables geometric mean, 95% CI and %CV_b (100 * √ (exp(SD²) -1)) will be provided, where the SD is the standard deviation of log-transformed data.

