10. STATISTICAL CONSIDERATIONS

The objectives of this study are to assess the safety and tolerability of single and repeat ascending doses of GSK2982772. No formal hypotheses will be tested.

An estimation approach will be used to describe PK of GSK2982772, where point estimates and corresponding 90% confidence intervals will be constructed.

[figure not shown]

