10.1. Sample Size Determination

No statistical techniques were used to calculate the sample size, and sample size is based on feasibility.

The primary objective of the study is safety, where the number of safety events are of interest. A maximum of 9 subjects will receive each active dose and; therefore, if 0/9 of a particular safety event in the GSK2982772 group is observed, the upper limit of the exact 95% CI indicates that a true incidence rate of 33.6% could not be ruled out. Whereas if 1/9 of the same safety event in the GSK2982772 group is observed, the upper limit of the exact 95% CI indicates that a true incidence rate of 48.2% could not be ruled out.

Using a Bayesian approach to determine the confidence interval around an observed safety event, we would assume a flat Beta (1,1) prior, and if we were to observe one safety event in 9 then the posterior distribution would be Beta (2, 9), as outlined below:

Bayesian Approach to Determine Confidence in a Safety Event.

Thus, we can be 95% certain that the true probability of the safety event lies between 0.04 and 0.39.

Pharmacokinetic Parameters

To date the pharmacokinetics of GSK2982772 have been studied up to 120 mg BID. The maximum between-subject coefficient of variation (CVb) for $AUC_{(0-\tau)}$ and C_{max} observed in study 200975 was 27.1 and 36.1 respectively.

Based on these estimates of variability, slightly more conservative for a cross-over study and a sample size of 9 completers in Cohort 2, it is estimated that the lower and upper bounds of the 90% confidence interval for the means of AUC and C_{max} will be within approximately 17.9% and 24.2% of the point estimate, respectively.

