10.4.2. PK Analyses

Endpoint	Statistical Analysis Methods
Secondary	
PK analyses will be described in the RAP.
 
The PK of TID and BID dosing on Day 1 in Part A will be evaluated. In Part B the comparisons of interest will be:
 
The PK profile following the 1st dose of the day following administration in the fed state (standard meal on Day 9 and high fat meal on Day 11) or in the fasted state (Day 14).
 
The pharmacokinetic profile following the 1st dose on Day 14 (fasted) and the 1st dose on Day 1 (fasted);
 
Pharmacokinetic data will be listed and presented in graphical form and will be summarized descriptively.
 
Statistical summaries of the PK parameter data will be the responsibility of

Endpoint	Statistical Analysis Methods
	
Clinical Statistics, GlaxoSmithKline.
 
Descriptive statistics (n, arithmetic mean, standard deviation, 95% CI, minimum, median and maximum,) will be calculated for all pharmacokinetic parameters by treatment. In addition, for loge-transformed variables geometric mean, 95% confidence interval and %CVb ($100 * \sqrt{\exp(SD_2) - 1}$) will be provided, where the SD is the standard deviation of log-transformed data.

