2.4. Statistical Hypotheses / Statistical Analyses

- The objectives of this study are to assess the safety and tolerability of single and repeat ascending doses of GSK2982772. No formal hypotheses will be tested.
- An estimation approach will be used to describe pharmacokinetics of GSK2982772, where point estimates and corresponding 90% confidence intervals will be constructed, unless otherwise stated.

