10.10.7. Pharmacokinetic Tables

Pharm	acokinetic: Tables				
No.	Population	IDSL / Example Shell	Title	Programming Notes	Deliverable [Priority]
Part A	(Cohort 1 – single a	scending dose,	3-way crossover): Pharmacokinetic Concentrations		
3.1.	Pharmacokinetic (Part A)	PK01	Summary of Plasma GSK2982772 Pharmacokinetic Concentration-Time Data (Part A)	Include column for 95% CI.	SAC
3.2.	Pharmacokinetic (Part A)	PK01	Summary of Plasma M8 (GSK3562183) Pharmacokinetic Concentration-Time Data (Part A)	Include column for 95% CI.	SAC
3.3.	Pharmacokinetic (Part A)	PK01	Summary of Plasma M9 (GSK2997852) Pharmacokinetic Concentration-Time Data (Part A)	Include column for 95% CI.	SAC
Part A	(Cohort 1 – single a	scending dose,	3-way crossover): Pharmacokinetic Parameters		
3.4.	Pharmacokinetic (Part A)	PK03	Summary of Derived Plasma GSK2982772 Pharmacokinetic Parameters (Part A)	Include columns for parameter, period, treatment, N, n, mean, 90% CI, standard deviation [SD], standard error [SE], median, minimum and maximum.	SAC
3.5.	Pharmacokinetic (Part A)	PK05	Summary of Log-Transformed Derived Plasma GSK2982772 Pharmacokinetic Parameters (Part A)	Include columns for parameter, period, treatment, N, n, geometric mean, 90% CI of geometric mean, standard deviation [SD] of logged data and %CVb.	SAC
Part B	(Cohorts 2, 3, 4 and	5 – repeat dose	e, sequential-group): Pharmacokinetic Concentrations		
3.6.	Pharmacokinetic (Part B)	PK01	Summary of Plasma GSK2982772 Pharmacokinetic Concentration-Time Data (Part B)	Include column for 95% CI and the SE.	SAC

20518	4
-------	---

Pharm	Pharmacokinetic: Tables					
No.	Population	IDSL / Example Shell	Title	Programming Notes	Deliverable [Priority]	
3.7.	Pharmacokinetic (Part B)	PK01	Summary of Plasma M8 (GSK3562183) Pharmacokinetic Concentration-Time Data (Part B)	Include column for 95% CI and the SE.	SAC	
3.8.	Pharmacokinetic (Part B)	PK01	Summary of Plasma M9 (GSK2997852) Pharmacokinetic Concentration-Time Data (Part B)	Include column for 95% CI and the SE.	SAC	
Part B	(Cohorts 2, 3, 4 and	5 – repeat dose	, sequential-group): Pharmacokinetic Parameters			
3.9.	Pharmacokinetic (Part B)	PK03	Summary of Derived Plasma GSK2982772 Pharmacokinetic Parameters (Part B)	Include columns for parameter, treatment, N, day, fed/fasted state, n, mean, 90% CI, standard deviation [SD], SE, median, minimum and maximum.	SAC	

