3.10.	Pharmacokinetic (Part B)	PK05	Summary of Log-Transformed Derived Plasma GSK2982772 Pharmacokinetic Parameters (Part B)	Include columns for parameter, treatment, N, day, fed/fasted state, n, geometric mean, 90% CI of geometric mean, standard deviation [SD] of logged data and %CVb. Do not summarise Tmax.	SAC	

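### The plan names fed/fasted, Day 14/Day 1 and CYP3A4-marker comparisons within participants but gives no interval for any of them, and SAP 8.1.2 and the tables disagree on 95% or 90% CIs for derived PK parameters

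*SAP*

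**What the plan says.** On comparisons, SAP 8.1.2 begins "In Part B the comparisons of interest will be" and lists first-dose PK on Day 9 (standard meal) and Day 11 (high-fat meal) against Day 14 (fasted), and first-dose PK on Day 14 against Day 1. Protocol 10.4.2 has the same list. Protocol 9.4.3 commits to comparing the 4β-hydroxycholesterol:cholesterol ratio on Day 14 with baseline.

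On outputs, SAP 8.1.2 specifies: "Descriptive statistics (n, arithmetic mean, standard deviation [SD] standard error [SE], 95% CI, minimum, median and maximum) will be calculated by treatment". In SAP 10.10.7, Table 3.9 is to "Include columns for parameter, treatment, N, day, fed/fasted state, n, mean, 90% CI" and Table 3.10 is to "Include columns for parameter, treatment, N, day, fed/fasted state, n, geometric mean, 90% CI of geometric mean". For the marker, SAP 6.2 promises a summary and a listing. Table 2.35 asks for an SE and a 95% CI, and its example shell in Appendix 11 has one row for Day -1/1 and one for Day 14 under each active dose.

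On the CI level, the two documents give both values:

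- **90%:** Protocol section 10 ("An estimation approach will be used to describe PK of GSK2982772, where point estimates and corresponding 90% confidence intervals will be constructed"); SAP 2.4 ("where point estimates and corresponding 90% confidence intervals will be constructed, unless otherwise stated"); the precision statement in Protocol 10.1 ("approximately 17.9% and 24.2% of the point estimate, respectively"); and SAP Tables 3.4, 3.5, 3.9 and 3.10.
- **95%:** Protocol 10.4.2 ("for loge-transformed variables geometric mean, 95% confidence interval and %CVb") and SAP 8.1.2, for raw and log-transformed parameters.

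The concentration tables (3.1 to 3.3 and 3.6 to 3.8) use 95% and agree with SAP 8.1.2, so the conflict is confined to derived parameters.

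**The concern.** The food and CYP3A4 secondary objectives ask how much a quantity changes within a person. A one-sample interval for each day reflects the spread between people on that day. The precision of the change depends also on how strongly a person's two values are correlated, and no planned table reports that correlation. A reader can form a point ratio from two geometric means in Table 3.10. The tables do not show whether a ratio near 1 means little effect or an imprecise estimate.

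The sponsor relies on these answers. Protocol 5.6 explains that the food assessment is built into this study in place of a separate one. The rationale for Amendment 01 makes an added contraceptive precaution depend on data from this marker.

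The CI-level conflict is editorial, but a programmer following the SAP text and one following the table specifications would print different limits for the same parameter.

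**Working it through.** **Inputs.** Between-subject CVs of 27.1% (AUC) and 36.1% (Cmax) and n = 9, all from Protocol 10.1. Quantiles with 8 degrees of freedom are t = 1.860 (90% CI) and t = 2.306 (95% CI).

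**Step 1: reproduce the protocol's precision.** Log-scale SD = √ln(1 + CV²), which is 0.2662 for AUC and 0.3500 for Cmax. The upper limit relative to the point estimate is exp(t × SD / √n) − 1.

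- AUC, 90%: 1.860 × 0.2662 / 3 = 0.165, giving 17.9%.
- Cmax, 90%: 1.860 × 0.3500 / 3 = 0.217, giving 24.2%.

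Both match Protocol 10.1. The same formula at n = 6 gives 24.5% and 33.4%, matching Protocol Table 2. (The column headed CVb in that table holds these log half-widths, for example 16.5% and 21.7%, and not the CVs of 27.1% and 36.1%.)

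**Step 2: the same quantities at 95%.**

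- AUC: 2.306 × 0.2662 / 3 = 0.205, giving 22.7%.
- Cmax: 2.306 × 0.3500 / 3 = 0.269, giving 30.9%.

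The log half-width grows by 2.306 / 1.860 = 1.24. The protocol's precision statement therefore agrees with the 90% in the tables and not with the 95% in SAP 8.1.2.

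**Step 3: what by-day intervals imply for a paired ratio.** Assume the same SD on both days and within-person correlation r. The SD of the within-person log difference is SD × √(2(1 − r)), so the 90% limits of the ratio are exp(±1.860 × SD × √(2(1 − r)) / 3) − 1. The documents give no r; the values below are assumptions.

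| r (assumed) | AUC lower, upper | Cmax lower, upper |
|---|---|---|
| 0 | −20.8%, +26.3% | −26.4%, +35.9% |
| 0.5 | −15.2%, +17.9% | −19.5%, +24.2% |
| 0.8 | −9.9%, +11.0% | −12.8%, +14.7% |

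All three rows are consistent with identical by-day intervals in Table 3.10.

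**Step 4: the same question through a within-subject CV.** The documents do not give this either. With assumed values of 10%, 15%, 20% and 25%, exp(1.860 × SDw × √(2/9)) − 1 gives +9.1%, +14.0%, +19.0% and +24.1%.

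**Step 5: search for a contrast.** SAP 6.2, 8.1.2 and 10.10.7, Table 2.35 and its shell specify no paired difference, geometric mean ratio, change from baseline or model for these three comparisons, and no interval for one.

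**The case against.** The strongest case against has five parts.

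- **No ratio analysis was promised.** Protocol 10.4.2 says PK data will be listed, plotted and summarised descriptively, no hypothesis is tested, and sample size rests on feasibility. This is right. The point is a gap in the estimation plan and does not contradict the protocol. But both documents adopt estimation with intervals, and the named comparisons are the quantities left without one.
- **Individual data are listed.** Listing 79 gives each participant's derived parameters, and the shell for Listing 65 has a per-participant ratio column, so someone could compute paired intervals later. That is true, but it leaves the choice of method and level to be made after the data are seen.
- **The Table 2.35 shell is only an example.** It shows N = 24 per dose, which fits no cohort. Its lack of a placebo row is therefore weak evidence that placebo will be left out. The lack of any change row stands, because the table specification and SAP 6.2 ask for none.
- **SAP 2.4 allows exceptions to 90%.** It does, and SAP 8.1.2 could be read as one, in line with Protocol 10.4.2. The tables then contradict that exception, so the wording does not settle the level.
- **It is late.** SAP 5.1 records that the PK stopping criteria were met at the end of Cohort 4, and the sponsor was unblinded throughout. Ratios added now are not prospective and should be labelled accordingly. They remain informative.

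**Conclusion.** Both parts stand. The three within-participant comparisons have no planned interval, and by-day intervals cannot supply one without the within-person correlation. At n = 9 and the protocol's CVs, the 90% upper limit for a paired ratio could be anywhere from +11.0% to +26.3% for AUC and from +14.7% to +35.9% for Cmax as the assumed correlation falls from 0.8 to 0. Those ranges rest on assumed correlations, equal SDs on the two days, and CVs that were the maximum seen in the earlier study. They show how little the planned tables say about the precision of the change; they do not predict it.

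The CI-level conflict rests on the documents alone: 17.9% and 24.2% at 90% against 22.7% and 30.9% at 95%. The protocol contains both levels. Within the SAP, 8.1.2 is the outlier for derived parameters.

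The change should be made, because it answers secondary objectives from data already collected. It does not affect the primary safety analysis.

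**What to change.** 1. For log AUC(0-7) and first-dose Cmax in the Part B TID cohorts, add within-participant geometric mean ratios by dose level with 90% CIs (paired or mixed model) for Day 9/Day 14, Day 11/Day 14 and Day 14/Day 1. The TID cohorts suffice because SAP 5.1 indicates that the Cohort 5 dose level was not needed. State that the fixed day order confounds food with day, and that the ratios were added after Cohort 4.
2. Add to Table 2.35 the within-participant Day 14/baseline geometric mean ratio of the marker with its CI, by treatment, including placebo where assayed.
3. Change SAP 8.1.2 to 90% CIs for derived PK parameters, keep 95% for concentrations as in their tables, and note in SAP Table 1 that the protocol contains both levels.
4. Clarify two points of wording. SAP 8.1.1.2 should say that first-dose Cmax and Tmax are also derived on Days 1, 9 and 11, since it now names only Day 14 for Part B. The SAP should also say that AUC(7-14), a listed food endpoint, cannot be fully observed on Days 9 and 11, where sampling ends at 12 h.

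The cost is a few lines of SAP text, one ratio table and one block in Table 2.35. No new data are needed, and the analysis remains estimation without a hypothesis test.
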